7.9.3.2 Movement Disorders Society Unified Parkinson's Disease Rating Scale (MDS-UPDRS)

The MDS-UPDRS is an MDS-sponsored revision of the UPDRS clinical rating scale for Parkinson's disease. It has been the most widely used scale to assess impairment and disability in PD. The MDS-UPDRS is a comprehensive 50 question assessment of both motor and non-motor PD symptoms. The assessment has four parts: Part I (non-motor experiences of daily living), Part II (motor experiences of daily living), Part III (motor examination) and Part IV (motor complications). Parts 1A, III and IV are assessed by the trained rater and Parts 1B and II are a self-administered patient questionnaire that is completed with or without the aid of the caregiver.

Each question is scored from 0 to 4 reflecting the subject's usual level of function; Normal, Slight, Mild, Moderate and Severe. Each part (I-IV) can be reported as sub-scores, or all parts can be reported as an overall score.

These items will be summarized from the MDS-UPDRS:

- MDS-UPDRS III subscore (On stim/On med) of tremor, rigidity, and bradykinesia questions where a side can be determined: 3.3 b, c, d, e (rigidity), 3.4 a, b (finger taps/bradykinesia), 3.15 a, b

(postural tremor of hands), 3.16 a, b (kinetic tremor of hands), and 3.17 a, b, c, d (rest tremor amplitude)

- MDS-UPDRS III (On stim/On med)
- MDS-UPDRS II: “best” and “worst” conditions
- MDS-UPDRS III speech question (On stim/On med) q 3.1
- MDS-UPDRS IV

Additionally, for those with mixed programming (one hemisphere with aDBS and one with cDBS), MDS-UPDRS III will be summarized by side in the On stim/On med condition.

Missing values

Missing data will be imputed using the methods of Goetz et. Al.⁸ The analysis will be performed on the CC analysis set when there is partial data meeting the requirements for imputation specified in Goetz et. Al. To provide valid part scores applicable across all Hoehn and Yahr (H&Y) stages when the same items are consistently missing, one missing item from Part I, one from Part II, three from Part III, but none from Part IV can be allowed. To provide valid part scores applicable across all H&Y stages when random item entries are missing, one missing item from Part I, two from Part II, seven from Part III, but none from Part IV can be allowed.

7.9.3.3 European Quality of Life – 5 Dimensions (EQ-5D-5L)

The European Quality of Life – 5 Dimensions, version 5L (EQ-5D-5L), is a standardized measure of health status developed by the EuroQol Group and a widely used validated tool to determine health-related quality of life. The EQ-5D descriptive system consists of 5 dimensions: mobility, self-care, usual activities, pain/discomfort, and anxiety/depression. Each dimension has 5 levels of severity: no problems, slight problems, moderate problems, severe problems, extreme problems. The subject will be asked to indicate his/her health state by selecting the most appropriate statement in each of the 5 dimensions. This decision results in a 1-digit number expressing the level selected for that dimension. The digits for 5 dimensions can be combined into a 5-digit number describing the respondent's health state. It should be noted that the numerals 1-5 have no arithmetic properties and should not be used as a cardinal score. In a second step, the responses to the five EQ-5D dimensions (i.e. an EQ-5D health state or profile) will be converted into a single number called an index value using the United Kingdom value set. The index value reflects how good or bad the health state is according to the preferences of the general population of a country/region.

The EQ-5D dimensions will be summarized as categorical measures and the index value and visual analog scale (VAS) will be summarized as continuous measures. The 5-digit number describing the respondent's health state will not be summarized.

⁸ Goetz, C.G., Luo, S., Wang, L., Tilley, B.C., LaPelle, N.R. and Stebbins, G.T. Handling Missing Values in the MDS-UPDRS. *Mov Disord.* 2015 Oct; 30(12): 1632-8, doi: 10.1002/mds.26153. Epub 2015 Feb 4.

Missing values

Missing data imputation will not be performed for the EQ-5D-5L.

7.9.3.4 Parkinson's Disease Sleep Scale 2 (PDSS-2)

The PDSS-2 assesses a wide spectrum of disease-specific sleep problems and is administered as a patient self-rating scale.

The PDSS-2 consists of 15 questions about various sleep and nocturnal disturbances which are to be rated by the patients using one of five categories, from 0 (never) to 4 (very frequent). PDSS-2 total score ranges from 0 (no disturbance) to 60 (maximum nocturnal disturbance).

Missing values

If less than 50% of the questions are missing, the PDSS-2 total score should be retained with the mean scale score of the items present used to impute a score for the missing items. These imputations will be performed on the Complete Case analysis set.

7.9.3.5 Wearable Data

Wearable data will be collected via the PKG Watch as a continuous measure of bradykinesia score (BKS) and dyskinesia score (DKS). A Fluctuation and Dyskinesia score (FDS) will also be derived from the wearable data. The analysis may include reliable data based on day or night on wrist count and all available data.

In addition to the main analysis of wearable data, a subgroup analysis will be performed for those with dyskinesias at least 25% of time. This will be defined from the MDS-UPDRS question 4.1, in the off medication, off stimulation state at the cDBS Baseline visit.

Missing values

Missing data imputation will not be performed with the wearable data.

7.9.3.6 Parkinson's Disease Questionnaire (PDQ-39)

The Parkinson's Disease Questionnaire is a self-completion Patient Reported Outcome (PRO) designed to address aspects of functioning and well-being for those affected by Parkinson's disease. There are 39 questions in the long form Parkinson's Disease Questionnaire, with 8 discrete domains:

- mobility (10 items, questions number 1 to 10)
- activities of daily living (6 items, questions number 11 to 16)
- emotional well-being (6 items, questions number 17 to 22)
- stigma (4 items, questions number 23 to 26)
- social support (3 items, questions number 27 to 29)
- cognitions (4 items, questions number 30 to 33)
- communication (3 items, questions number 34 to 36)
- bodily discomfort (3 items, questions number 37 to 39)

Patients are asked to think about their health and general well-being and to consider how often in the last month they have experienced certain events (e.g. difficulty walking 100 yards). Patients are asked to indicate the frequency of each event by selecting one of 5 options (Likert Scale): never/occasionally/sometimes/often/always or cannot do at all. *Never* is given a score of 0, and *always or cannot do* is given a score of 4, and the remaining options are scored between 1 and 3.

Each domain is calculated as a scale from 0 to 100, where 0 represents no problem at all and 100 represents the maximum level of problem. The formula for scoring each domain is:

$$\frac{\text{sum of scores of each question in domain}}{4 * \text{number of questions in domain}} \times 100$$

The PDQ-39 Summary Index (SI) and the 8 subscales will be summarized for this outcome⁹. In addition to the SI and its 8 subscales, the PDQ-39 speech questions 34 and 35 will be summarized individually as well.

The PDQ-39-SI is scored as:

$$\frac{\text{sum of all domain scores}}{8}$$

Missing values

If the response to a question is missing, no scale score is calculated for that individual for that domain. This precludes the calculation of the PDQ-39 summary index score.

7.9.3.7 Parkinson's Disease (PD) Home Diary

The Parkinson's Disease Home Diary is a standard home diary to assess functional status in patients with PD. In 30-minute intervals, patients record whether they were in the "On" condition, with or without dyskinesia, "Off" condition, or asleep. In the On condition with dyskinesia, patients record whether they were On with troublesome or non-troublesome dyskinesia.

These items will be summarized from the PD Home Diary:

- "On" time without troublesome dyskinesia
- "On" time without dyskinesia
- "On" time with non-troublesome dyskinesia
- "On" time with troublesome dyskinesia
- "Off" time

⁹ Jenkinson, C., Fitzpatrick, R., Peto, V., Dunnett, S., Kelly, L. and Morley, D. The Parkinson's Disease Questionnaires User Manual, Fourth Edition. Health Services Research Unit, University of Oxford. 2018

- Asleep time

The analysis will use the FAS as described in Section 7.1.3. The PD Home Diary will be collected for at least 3 consecutive days (24 hour “periods”) prior to each visit to evaluate the PD Home Diary additional objectives. Diary periods will be defined starting with the first completed diary record which is no more than 14 days prior to the visit. Complete diary periods are defined as any diary period where at least 21 hours (defined as 42 30-minute records) of diary were completed during the 24-hour period, and only complete periods will be used for analysis. If the diary is collected for more than 3 complete periods, up to 7 which are closest to the visit will be used for the analysis, while if a subject has zero complete periods, their diary will be considered missing. Diaries with at least 1 complete period available will be used for analysis. Included days cannot be more than 14 days prior to the visit. Data from non-contiguous complete periods may be used in the analysis.

The change in in daily averages from cDBS to aDBS will be computed for each item, for each subject. The overall standard deviation of the change will be computed for the FAS.

Missing values

If 5% of the data or fewer are missing (as defined in section 7.9.1.4) for the analysis, no imputation will be used and the data will be analyzed as specified in the previous section. Otherwise, if missing data are observed, multiple imputation will be used for the analysis of each item from the PD Home Diary.

Prior to the MI, the distribution of the continuous variables will be assessed for normality (using the Shapiro-Wilk test) to determine whether regression ($P \geq 0.05$) or predictive mean matching ($P < 0.05$) multiple imputation will be used for each variable. First, multiple imputation will be applied to impute missing values in continuous hours of each item on the PD Home Diary for each mode separately (aDBS single threshold, aDBS dual threshold). Variables for target site (STN or Gpi) and cDBS hours each applicable item will be considered for the model. The fully conditional specification (FCS) method within SAS (version 9.4 or higher) with 5 repetitions and 100 burn-in iterations will be used for imputation. No limits will be defined for imputed values. Following imputation, the change in in daily averages from cDBS to aDBS will be computed for each item, and the estimate and standard error of the change will be determined for each imputation. These will be combined into one result to estimate the change and standard error using MI analysis methods.

Supporting analyses

Sensitivity analyses will be conducted using the CC Analysis Set.

7.9.3.8 Patient Preference

Patient preference for aDBS vs. cDBS and Single vs. Dual Threshold aDBS modes (if both were evaluated) will be assessed by a Medtronic-developed questionnaire.

The questionnaire has three parts, the first assessing subject preference for aDBS as compared with the cDBS therapy they received before starting the study, to which subjects can reply that they strongly

prefer aDBS, somewhat prefer aDBS, no preference between aDBS and cDBS, somewhat prefer cDBS, or strongly prefer cDBS. The specific questions asked in part I are displayed in Figure 7-1.

The second part assesses subject blinding. Subjects report which aDBS mode they believe they received in the relevant period, why they believe that to be true, and how certain they are about their assessment. The specific questions are displayed in Figure 7-2.

The third part assesses subject preference for aDBS mode among subjects receiving therapy with both aDBS modes, to which subjects can reply that they prefer the first aDBS mode received, the second aDBS mode received, no preference, or do not know. The questions asked in part III are displayed in Figure 7-3.

Figure 7-1. Evaluation of aDBS therapy as compared to DBS therapy received prior to study start

Section I: Evaluation of the DBS Therapy Received Over the Past 14 Days

Instructions: We are interested in your evaluation of the deep brain stimulation (DBS) therapy you received over the past 14 days and would like you to compare it to the DBS therapy you were receiving before you joined the research study. Think about how effective the therapy was on your disease-related symptoms (examples: shaking, slowness, stiffness) and any side effects (examples: trouble swallowing, change in mood, tingling) caused by the DBS therapy you are receiving. For each question, please place a single check mark next to the response you feel best represents your experience and preferences.

Overall, do you prefer the DBS therapy you received during the past 14 days or the DBS therapy you were receiving prior to joining the research study

- Strongly prefer the DBS therapy received during the last 14 days.
- Somewhat prefer the DBS therapy received during the last 14 days.
- No preference between the two.
- Somewhat prefer the DBS therapy I was receiving prior to joining the research study.
- Strongly prefer the DBS therapy I was receiving prior to joining the research study.

Based on your improvement in movement symptoms (examples: slowness, stiffness, difficulty with speech, walking, balance, tremor) alone, do you prefer the DBS therapy you received during the past 14 days or the DBS therapy you were receiving prior to joining the research study

- Strongly prefer the DBS therapy received during the last 14 days.
- Somewhat prefer the DBS therapy received during the last 14 days.
- No preference between the two.
- Somewhat prefer the DBS therapy I was receiving prior to joining the research study.
- Strongly prefer the DBS therapy I was receiving prior to joining the research study.

Based on side effects (examples: trouble swallowing, change in mood, tingling) alone, do you prefer the DBS therapy you received during the past 14 days or the DBS therapy you were receiving prior to joining the research study

- Strongly prefer the DBS therapy received during the last 14 days.
- Somewhat prefer the DBS therapy received during the last 14 days.
- No preference between the two.
- Somewhat prefer the DBS therapy I was receiving prior to joining the research study.
- Strongly prefer the DBS therapy I was receiving prior to joining the research study.

Based on symptom fluctuations alone, do you prefer the DBS therapy you received during the past 14 days or the DBS therapy you were receiving prior to joining the research study

- Strongly prefer the DBS therapy received during the last 14 days.
- Somewhat prefer the DBS therapy received during the last 14 days.
- No preference between the two.
- Somewhat prefer the DBS therapy I was receiving prior to joining the research study.
- Strongly prefer the DBS therapy I was receiving prior to joining the research study.

Figure 7-2. Blinding

Section II: Blinding

NA, Subject is on CIP v2.0

1. In this period (past 30 days), which adaptive DBS mode do you believe was used?

- DUAL THRESHOLD
- SINGLE THRESHOLD
- I DON'T KNOW

2. Why do you believe that?

3. How sure are you about your belief?

- NOT SURE AT ALL, JUST GUESSED
- FAIRLY SURE
- ENTIRELY SURE

Figure 7-3. Comparison of aDBS modes**Section III: Comparison of the Adaptive DBS Modes Used in this Research Study**

Instructions: You received 2 types (modes) of adaptive deep brain stimulation (DBS) therapy during this research study. We are interested in your evaluation of the two different modes. Think about how effective the therapy was on your disease-related symptoms (examples: shaking, slowness, stiffness) and any side effects (examples: trouble swallowing, change in mood, tingling) caused by the DBS therapy you received. For each question, please place a single check mark next to the response you feel best represents your experience and preferences.

Which adaptive DBS mode do you prefer

- Mode 1 (The first type of adaptive DBS you received).
- Mode 2 (The second type of adaptive DBS you received).
- No preference.
- Do not know.

Which adaptive DBS mode best controlled your disease-related symptoms (examples: shaking, slowness, stiffness)

- Mode 1 (The first type of adaptive DBS you received).
- Mode 2 (The second type of adaptive DBS you received).
- No preference.
- Do not know.

Which adaptive DBS mode resulted in the least number of side effects (examples: trouble swallowing, change in mood, tingling)

- Mode 1 (The first type of adaptive DBS you received).
- Mode 2 (The second type of adaptive DBS you received).
- No preference.
- Do not know.

Missing values

Missing data imputation will not be performed with the patient preference objective.

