If only one hemisphere has LFP Alpha - Beta signal $\geq 1.2\mu\text{Vp}$ when setting up Single Threshold mode, the clinician should configure adaptive therapy in only that hemisphere with LFP Alpha - Beta signal $\geq 1.2\mu\text{Vp}$.

- cDBS should be setup in the hemisphere with LFP Alpha - Beta signal $< 1.2\mu\text{Vp}$ (set to Passive Sensing, if possible).
- Note: that the stimulation electrode(s) or cathode(s) in the hemisphere set to cDBS is not constrained to a sensing configuration.

If one aDBS mode cannot be set up, the subject should continue with the study using only the mode that can be set up and the subject will not be randomized.

If neither aDBS mode can be set up, the subject will be exited from the study following the process in [Section 9.19](#), including uploading the programming session, with BrainSense data included in the JSON session data report, to Medtronic via CDU. No further study-related procedures will be completed, and subjects will be followed according to the center's standard procedures.

Following each aDBS setup visit day, the programming sessions, with BrainSense data included in the JSON session data report, will be uploaded to Medtronic via CDU.

Once aDBS is set up, and prior to the subject leaving the study center On aDBS, the subject's commercially available Patient Programmer System will be replaced with an investigational-marked Patient Programmer System, and the subject will be given the investigational patient labeling. The

Medtronic Business Restricted

clinician or appropriately delegated study personnel will assist the subject to pair the investigational Patient Programmer System with the INS.

Subjects will be instructed on how to pause aDBS any time they feel like the therapy is not working for them by selecting Pause Adaptive Therapy. This Pause Adaptive Therapy (amplitude last delivered in that group prior to starting aDBS therapy (i.e. the suspend amplitude)) is defined by the clinician as part of the aDBS setup process, following the streaming transition schemes testing and prior to starting adaptive therapy. Subjects will notify the investigator when they pause aDBS to assess the scenario and need for any adjustments.

If the visit occurs over 2 days, the clinician may program the subject to one aDBS mode between visit day 1 and visit day 2.

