At the end of the aDBS Setup Visit, the subject may resume taking their normal PD medication. The physician may also be surveyed to understand rationale for programming settings. The investigator may determine that additional aDBS programming adjustments are needed for one or both of the aDBS modes, or the subject may proceed directly to randomization, or. If additional adjustment is planned for only one aDBS mode, the investigator will send the subject home in that mode for as much time as needed within the aDBS Adjustment Period. If additional adjustment is planned for both aDBS modes, the investigator will send the subject home in one of the aDBS modes to start the aDBS Adjustment Period. The investigator and subject will determine how and when to adjust the other aDBS mode within the aDBS Adjustment Period (if applicable). Event markers may be set up to further capture information about the patient's out of clinic experience with aDBS.

Every attempt will be made to blind the subject to the aDBS mode being adjusted. The clinician should set on the investigational Clinician Programmer the group names of the aDBS modes being adjusted in a manner which will not unblind the subject. For example, "aDBS 1" and "aDBS 2" or "aDBS" and "Do not use." These group names will be displayed on the investigational Patient Programmer.

9.9.2. aDBS Adjustment Period (optional)

0-60 days after aDBS setup complete

Additional visits for the clinician to adjust settings for one or both aDBS modes may be conducted as needed for up to 60 days following the final aDBS setup visit to ensure the aDBS mode(s) will be acceptable to the subject. These visits will be completed either at the study center, by telephone or telehealth/video consult. The subject will remain blinded to the programmed aDBS mode. Any aDBS adjustment visit will be recorded as an unscheduled visit (see [Section 9.13](#)). The physician may also be surveyed to understand rationale for programming settings.

If programming sessions or device interrogations occur, these sessions with BrainSense data included in the JSON session data report, will be uploaded to Medtronic via CDU.

Medtronic Business Restricted

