9.9.3. Randomization

Day 0 (no greater than 60 days after aDBS setup complete)

Randomization may occur at the aDBS setup visit, at an unscheduled visit during the aDBS Adjustment Period, or as a standalone visit. All subjects for whom aDBS was set up will complete this visit.

The investigator will assess each aDBS mode that was set up utilizing the aDBS Global Impression of Change (GIC) provided in [Appendix A - aDBS Global Impression of Change Score \(GIC\)](#). Efficacy and side effects are assessed on a scale from 1 to 21. The lower the score the better the efficacy and the less side effects. A score of 8 or less indicates the aDBS mode is acceptable. The investigator will also ensure that the subject is comfortable remaining in the aDBS mode(s) for the duration of the trial.

If only one aDBS mode was set up for a subject, they will not be randomized, but the physician should still complete the aDBS GIC and data collection for the visit.

Data will be collected, including the following:

- Concomitant medications
- GIC value for each aDBS mode that was set up
- Adverse Event and device deficiency assessment

For subjects in whom both aDBS modes are acceptable as compared to cDBS (using the aDBS GIC), unblinded site personnel will obtain the randomization assignment via Remote Data Capture (RDC). The randomization assignment can be obtained upon completion of the aDBS GIC and randomization CRFs.

Randomization will occur to one of two possible treatment sequences if both aDBS modes are acceptable as compared to cDBS (using the aDBS GIC) (dual threshold mode followed by single threshold mode or vice versa) and will be stratified by target site location (STN/GPi). The two sequences will be randomly permuted in blocks of two and four. If an aDBS mode is unacceptable as compared to cDBS (using the aDBS GIC), that subject will be assigned the mode which was acceptable. The randomization schedule will be prepared by Medtronic and it will be maintained at Medtronic. Subjects will continue to be blinded to the aDBS mode during the aDBS Evaluation Phase. If the blind is broken, document the reasons for unblinding in the subject's source documentation and report as a deviation.

Following randomization, the clinician will program one group to the randomized aDBS mode.

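### The mode-preference items name the two aDBS modes only by order received, with no Evaluation Phase anchor, so some answers could be credited to the wrong mode

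*SAP*

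**What the plan says.** SAP 7.9.3.8 describes a three-part questionnaire. In the third part, given to subjects treated with both modes, the answers are described as ones "to which subjects can reply that they prefer the first aDBS mode received, the second aDBS mode received", with no preference and do not know as the other options. Figure 7-3 introduces the part with "You received 2 types (modes) of adaptive deep brain stimulation (DBS) therapy during this research study". It then offers "Mode 1 (The first type of adaptive DBS you received" and the matching Mode 2 option for three items: overall preference, symptom control and side effects. Neither the figure nor the text ties Mode 1 or Mode 2 to an Evaluation period or to a named mode.

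The other two parts of the form are anchored in time. Section I refers to the past 14 days. Section II asks "In this period (past 30 days), which adaptive DBS mode do you believe was used".

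The protocol allows aDBS use at home before randomization:

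- Section 9.9.1: if Setup takes two days, "the clinician may program the subject to one aDBS mode between visit day 1 and visit day 2".
- Section 9.9.1: if both modes need more adjustment, "the investigator will send the subject home in one of the aDBS modes to start the aDBS Adjustment Period". The investigator and subject then decide how and when to adjust the other mode.
- Section 9.9.2: "Additional visits for the clinician to adjust settings for one or both aDBS modes may be conducted as needed for up to 60 days".

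Only afterwards does section 9.9.3 randomize the sequence, "dual threshold mode followed by single threshold mode or vice versa", stratified by target site alone.

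**The concern.** The form identifies treatment by order alone, and a subject can have met the modes in two different orders: one during Setup and Adjustment, and one in the Evaluation Phase. The introduction speaks of the whole study, so a literal reader could count from the first home use. The subject is blinded throughout and cannot correct the label by mode name. One of the two example naming schemes for the Adjustment Period in protocol 9.9.1 shows the groups as aDBS 1 and aDBS 2 on the patient programmer, which is close to the form's Mode 1 and Mode 2. Under protocol 9.15.9 the form may also be completed away from the clinic, up to 7 days before the visit.

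If the answers are decoded by the randomized sequence, which is the natural choice but is not written down, an answer given in Adjustment order is counted for the other mode. With the sequence randomized independently of home order, such errors run in both directions and dilute a true preference toward 50:50. Nothing in the planned summary would reveal it.

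A smaller gap goes with this. Protocol Table 3 schedules the preference questionnaire at both Evaluation visits, and the SAP does not say that Section III is taken only from Evaluation Visit 2. A subject who used both modes in Adjustment could already consider Section III applicable at Visit 1.

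**Working it through.** The plan states no figure on this point, so there is nothing to reproduce. The check compares the two possible orders and then sizes the effect under stated assumptions.

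**Who is exposed**

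- *No home use before randomization.* Protocol 9.9.1 lets a subject go straight to randomization. First and second can then only mean Evaluation periods 1 and 2. No conflict.
- *Home use of both modes, same order as the randomized sequence.* Either reading gives the same decoding. No conflict.
- *Home use of both modes, opposite order.* Counting from Adjustment reverses the answer. This is the main exposed group.
- *Home use of one mode only, the other mode first in Evaluation.* A reversed answer requires the blinded subject to notice that Evaluation period 1 is a different type from the one used at home. Possible, but less likely.

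**Inputs**

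- Two sequences in permuted blocks of two and four (protocol 9.9.3), read as 1:1. No link to home order is stated, so about half of the subjects who used both modes at home are expected to have the opposite order in Evaluation.
- f: share of mode-naming subjects who used both modes at home before randomization. Not in the documents; assumed.
- c: share of the opposite-order subjects who answer by the earlier order. Not in the documents; assumed.
- Answers of no preference or do not know cannot be reversed and are left out.

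**Formulas**

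- Reversed share: m = 0.5 × f × c.
- If the true share preferring one mode is p and reversal is equally likely whichever mode is preferred, the observed share is p(1−m) + (1−p)m.
- The observed difference between modes is therefore (1−2m) times the true difference.

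**Results for a true 80:20 split**

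| f × c | m | 1−2m | Observed split |
|---|---|---|---|
| 0.0625 (f = c = 0.25) | 3.1% | 0.94 | 78:22 |
| 0.20 | 10% | 0.80 | 74:26 |
| 0.25 (f = c = 0.5) | 12.5% | 0.75 | 72.5:27.5 |
| 0.50 | 25% | 0.50 | 65:35 |
| 1.00 | 50% | 0 | 50:50 |

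For m = 10%: 0.80 × 0.90 + 0.20 × 0.10 = 0.72 + 0.02 = 0.74. The difference falls from 60 to 48 percentage points, and 48/60 = 0.80. The last row needs every such subject to have used both modes at home and every opposite-order subject to answer by that order. It is a bound, not an expectation.

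**The case against.** The best defense is that context points the subject to the Evaluation Phase. SAP 7.9.3.8 limits the comparison to subjects in whom both modes were evaluated. Section III follows directly on a question about the past 30 days. At randomization the group names become aDBS and Do not use (protocol 9.9.3), and the change of mode at Evaluation Visit 1 is an explicit reprogramming (protocol 9.10.1). The naming example in protocol 9.9.1 also offers aDBS and Do not use as an alternative to numbered labels. All of this makes the study-wide reading less likely. It does not supply the missing anchor, and Section III remains the one part of the form without a time frame.

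A reader might infer that Section III is the only patient-reported comparison of the modes. The documents do not support that. The patient's and physician's preferred mode, with the reason, is recorded at Evaluation Visit 2 (protocol 9.10.2), and Section I rates the therapy of each Evaluation period against earlier cDBS. The first is a joint choice and the second is indirect, so neither directly checks the head-to-head items on symptom control and side effects.

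A reader might also infer that about half of all subjects with a home Adjustment Period are miscounted. That goes too far, since a subject sent home in one mode only would have to see through the blind for the answer to flip.

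The point that this outcome is peripheral stands. The objective listed in protocol 4.1.4 and SAP 4.4 is preference between aDBS and cDBS. Single-versus-dual preference appears only where the instrument is described, and SAP 7.9.3 plans no hypothesis tests on additional objectives.

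**Conclusion.** The concern holds as a limited, correctable labeling fault. As written, the form allows answers on three items to be credited to the wrong mode, and the SAP has no decoding rule that would expose it. The likely effect is dilution of a real preference by the factor 1−2m. The size is unknown: the documents give neither the frequency of home use of both modes nor any evidence of misreading. The 10% illustration (80:20 seen as 74:26) is an assumption. It also rests on 1:1 sequences unrelated to home order and on reversal being equally likely for either preferred mode.

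It would be wrong to conclude that the mode-preference results carry no information, or that the choice of mode for long-term follow-up is compromised. That choice rests on clinician and patient preference recorded at the visit (protocol 9.10.2), not on the decoding of Section III. Overall preference can be partly cross-checked against that same record.

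**What to change.** On any forms still to be completed, define Mode 1 as the aDBS used from Day 0 to Evaluation Visit 1, and Mode 2 as the aDBS used from Evaluation Visit 1 to Evaluation Visit 2, with the subject's own dates filled in. Add a line asking the subject to disregard use during Setup and Adjustment.

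In SAP 7.9.3.8, state that Section III is taken from Evaluation Visit 2 and that Mode 1 and Mode 2 are decoded to dual or single threshold by Evaluation period.

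For completed forms, add a sensitivity summary restricted to subjects with no home use of aDBS before randomization or whose home order matched their randomized sequence. Report agreement between the overall-preference item and the preferred mode recorded at Evaluation Visit 2.

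The cost is a few lines on a sponsor-developed form, a paragraph in the SAP and a small extra table. Wording will differ slightly between earlier and later forms. The form has a tick box for subjects on an earlier protocol version, so it may already have been in use for some time and the rewording may reach few subjects; the SAP rule and sensitivity summary then matter more. Home order may not be recoverable for everyone, because adjustment visits can be held by telephone and programming data are uploaded only when a session or interrogation takes place (protocol 9.9.2). The summary should say how many subjects could not be classified.
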